2.13.4 Dose proportionality

Analysis of dose-proportionality will be performed if at least three doses of LTT462 are investigated.

Cmax and AUC will be used for dose proportionality analysis using the power model (Gough 1995). The power model empirical relationship between a PK parameter and dose is of the form

 $PK = Exp(\alpha)(dose)^{\beta},$

where "PK" represents the PK parameter AUCinf or Cmax. For analysis, this equation is logtransformed (natural log), obtaining the equation

$$\log_e(PK) = \alpha + \beta \log_e(Dose),$$

The slope beta measures the dose-proportionality between Dose and the PK parameter

To test for dose proportionality, the confidence interval criteria for assessment of dose proportionality from Smith et al. (2000) will be used. The a *priori* acceptance range for the slope, according to Smith, is given by

$$1 + \frac{Ln(0.8)}{Ln(dose_ratio)} \langle \beta \langle 1 + \frac{Ln(1.25)}{Ln(dose_ratio)} \rangle$$

Where 1.25 and 0.8 are the critical *a priori* values suggested by regulatory authorities for any bioequivalence problem after a data log transformation, and "*dose_ratio*" is the ratio of the largest to the smallest dose. Dose proportionality can be claimed if the 90% confidence interval for the slope is entirely contained within this a *priori* range.

2.14 Biomarkers

As a project standard, Novartis Oncology BDM will analyze only biomarkers collected in the clinical database.

There may be circumstances when a decision is made to stop sample collection, or not perform or discontinue the analysis of blood / archival tumor samples / fresh tumor biopsies / fine needle aspirates due to either practical or strategic reasons (e.g. issues related to the quality and/or quantity of the samples or issues related to the assay). Under such circumstances, the number of samples may be inadequate to perform a rigorous data analysis and the available data will only be listed and potentially summarized.

2.14.1 Outline of data analysis

Additional analyses that may be performed after the completion of the end-of-study CSR will be documented in separate reports. These analyses may include but are not limited to the meta-analysis of data from this study combined with data from other studies or the analysis of biomarkers generated from samples collected during the study but analyzed after the database lock and completion of the CSR. The data analysis will be described in an addendum of the SAP or in a stand-alone analysis plan document, as appropriate.

2.14.2 Analysis data set

The Full Analysis Set will be used for all biomarker analysis. Assessment of association between biomarker and safety data will be conducted using the Safety Set.

2.14.3 General data handling

The last assessment before the first dose administration (pre-dose) will be used as baseline value. For assessments performed in tumor biopsies, fresh biopsy results will be used for baseline when both archived and fresh tumor samples are available. When more than one biomarker data are available for a subject at any time point, the mean of the replicate values will be used for all statistical analyses.

2.14.4 Dual specificity phosphatase 6 (DUSP6)

For assessment of PD effects of LTT462 in tumor, pre- and post- treatment tumor biopsies will be examined for expression of DUSP6. For assessment of PD effects in blood, levels of DUSP6 will be measured in samples isolated concomitantly with those collected for PK measurements.

Novartis	Confidential	Page 23
SAP	13-May-2019 (11:03)	CLTT462X2101

2.14.4.1 Handling of data

Percent Change in DUSP6 Expression is derived from the Relative Expression Ratio (RER), calculated according to the 'Comparative CT Method' described in Applied Biosystems User Bulletin #13 (2001) and consistent with the model described in (Pfaffl and Hageleit 2001). In this method, Δ CT is computed by subtracting the CT of a Reference Gene from the CT of DUSP6 for both Baseline and Post-Baseline Samples. RER is calculated by raising 2.0 to an exponent computed by subtracting the (Δ CT) of the Baseline Sample from (Δ CT) of the Post-Baseline Sample. RER is transformed by subtracting 1.0, such that expression increases and decreases are indicated when %Change is greater than or less than zero, respectively.

2.14.4.2 Deriving change from baseline in DUSP6 expression

Denoting the baseline (Δ CT) of one patient as **B** and the post-baseline as **PB**, then

• RER = $2^{(B-PB)}$

% Change in expression relative to Baseline = (RER -1)*100

2.14.4.3 Biomarker data reports

Type of sample (time point)	Biomarker	Biomarker assay	Table	Figure
Tumor	DUSP6		- Summary of baseline and percentage change (absolute and fold) from baseline in DUSP6 expression. (descriptive statistics include: mean, geometric mean, std, %CV, median, min-max)	- Waterfall plot to depict the change from baseline in DUSP6 expression annotated with the BOR - longitudinal plot of DUSP6 expression levels over time
Blood	DUSP6		- Summary of baseline and percentage change (absolute and fold) from baseline in DUSP6 expression. (descriptive statistics include: mean, geometric mean, std, %CV, median, min-max)	- Waterfall plot to depict the change from baseline in DUSP6 expression annotated with the BOR - longitudinal plot of DUSP6 expression levels over time

Table 2-10Biomarker data reports

Novartis	Confidential	Page 24
SAP	13-May-2019 (11:03)	CLTT462X2101

2.14.5 Advanced analysis methods

Additional analyses that may be performed after the completion of the final CSR will be documented in separate analysis reports. These analyses may include but are not limited to the meta-analysis of data from this study combined with data from other studies or the analysis of biomarkers generated from samples collected during the study but analyzed after the database lock and completion of the CSR. The data analysis will be described in a separate analysis plan document and may be included in the CSR.

3 Interim analysis

No formal interim analyses are planned. However, the dose escalation design foresees that decisions based on the current data are taken before the end of the study. More precisely, after each cohort in the dose escalation part, the next dose of LTT462 has to be chosen depending on the observed data. Details of this procedure and the process for communication with Investigators are provided in Section 6.2.3 of the study protocol.

Cumulative study data (including safety, tolerability, preliminary anti-tumor activity, PK, and PD) will be reviewed on an ongoing basis by Novartis and study investigators.

4 Sample size calculation

4.1 Dose-escalation part

Initially, cohorts of 1 to 3 evaluable patients will be enrolled in the dose-escalation part. Upon observation of specific toxicities, cohorts of 3 to 6 evaluable patients will be enrolled including at least six patients at the MTD/RDE level, as described in Section 6.2.3. Multiple cohorts may be sequentially enrolled to the same dose level. Additional cohorts of 1 to 6 patients may be enrolled at any dose level below the estimated MTD/RDE for further elaboration of safety and pharmacokinetic parameters as required. At least 21 patients are expected to be treated in the dose escalation part, for the model to have reasonable operating characteristics relating to its MTD recommendation. In the event that a lower dose is recommended for the use in the dose expansion without identification of the MTD, then the sample size may be smaller than 21.

Novartis SAP	Confidential 13-May-2019 (11:03)	Page 25 CLTT462X2101

Novartis SAP	Confidential 13-May-2019 (11:03)	Page 26 CLTT462X2101

5 Changes in planned analysis

Changes to planned analyses will be documented in section 9.8.3 of the CSR..

6 Appendix

6.1 Baseline

Baseline is the last available and valid assessment performed or value measured before the first administration of LTT462, unless otherwise stated under the related assessment section. Baseline can be the day before first treatment administration or the same day as first treatment administration if a pre-dose assessment/value is available (e.g., PK samples, samples for biomarkers).

Novartis	Confidential	Page 27
SAP	13-May-2019 (11:03)	CLTT462X2101

If time is recorded for the first treatment dose and for a specific assessment performed the day of first dose, this assessment will be considered as baseline only if it is actually performed before the first dose, as checked using both times.

If time is not recorded, a specific assessment performed the day of first dose administration will be considered as baseline if, according to protocol, it should be performed before the first dose.

Patients with no data on a particular parameter before the first treatment administration will have a missing baseline for this parameter.

6.2 Handling of missing and partial dates

For patients not known to have died prior to the cut-off date:

All events (e.g. AEs and concomitant medications) that started before or on the cut-off date, and with end date missing or after the cut-off date will be reported as continuing at the cut-off date. For these events, the end date will not be imputed.

For patients known to have died prior to or on the cut-off date:

All events (e.g. AEs and concomitant medications) that started before or on the cut-off date, and with end date missing or after the cut-off date will have the end date imputed to the date of death. For these events, the imputed end date will not appear in the listings.

If imputation of an end date is required for a specific analysis (e.g. a dose administration record with missing end date, or last date of study treatment is after the cut-off date), the end date will be imputed to the cut-off date in order to calculate e.g., the duration of exposure to study treatment. The imputed date will be displayed and flagged in the listings.

SAP 13-May-2019 (11:03) CLTT	462X2101

Novartis	Confidential	Page 29
SAP	13-May-2019 (11:03)	CLTT462X2101

7 References

Brookmeyer R and Crowley J (1982). A Confidence Interval for the Median Survival Time, *Biometrics* 38, 29 - 41.

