2.2 General definitions

Study drug and study treatment

Study drug and study treatment refer to LTT462 and are used interchangeable.

Date of first/last administration of study drug and study treatment

The date of first (last) administration of study treatment is derived as the first (last) date when a non-zero dose of study treatment LTT462 was administered and recorded on the Dosage Administration Record panel. For the sake of simplicity, the date of first (last) administration of study treatment will also be referred as start (last) date of study treatment.

Study day

The study day for all assessments/onset of events will be calculated using the start date of study treatment as reference. For assessments/events occurring on or after the start date of study treatment, study day will be calculated as:

Novartis	Confidential	Page 8
SAP	13-May-2019 (11:03)	CLTT462X2101

Study day (days) = Event date - Start date of study treatment + 1

Therefore, the first day of study treatment is study day 1.

For all assessment/onset of events occurring prior to the start of the study treatment, study day will be negative and will be calculated as:

Study day (days) = Event date – Start date of study treatment

On-treatment assessment/event

An on-treatment assessment/event is defined as any assessment/event in the time interval from the start date of LTT462 treatment until the last date of LTT462 treatment + 30 days inclusive.

LTT462 dose interruption

Study drug dose interruption is defined as a "total daily dose" equal to zero, between the first and last non-zero doses, following a non-zero total daily dose. This applies to any regimen, in our case QD and independently of the reason for interruptions.

LTT462 dose reduction

Time points at which the dose change flag is checked and the total daily dose is nonzero.

If the total daily dose at that time point is lower than the total daily dose at the time that the last non-zero dose was administered then the dose change is identified as a dose reduction.

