2.8.1 Study treatment

Last date of exposure to LTT462 is the last date of study treatment.

Study treatment will be summarized in terms of duration of exposure to study treatment, cumulative/average daily study drug dose, study drug intensity (DI).

- Duration of exposure (days): last date of exposure to study treatment first date of study treatment + 1 (periods of interruption are not excluded)
- Cumulative dose (mg): sum of all total daily doses of study drug taken by a patient
- Cumulative planned dose (*mg*): sum of all doses of study drug that was intended to have been taken during the treated period by a patient
- DI (mg/day): cumulative dose (mg)/number of doses scheduled per protocol during treatment period
- Relative DI: Cumulative dose (mg)/Cumulative planned dose (mg)

The duration of exposure to study treatment will also be summarized following the categories: <4, <=4, <=8, <=12, <=16, <=24 weeks.

Relative RDI will also be summarized following the categories: $<0.5, 0.5-<0.75, 0.75-<0.9, 0.9-<1.1, \ge 1.1$ for each study drug.

A listing of patient's dose administration records will be presented.

Novartis	Confidential	Page 12
SAP	13-May-2019 (11:03)	CLTT462X2101

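### SAP 6.2 imputes a missing dose end date to the data cut-off even for patients who died or stopped treatment earlier, which overstates their duration of exposure

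*SAP*

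**What the plan says.** SAP 6.2 (Handling of missing and partial dates) has two rules that matter here.

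- **Events in patients known to have died.** The rule covers "All events (e.g. AEs and concomitant medications) that started before or on the cut-off date". If the end date is missing or falls after the cut-off, such events "will have the end date imputed to the date of death".
- **End dates needed for a specific analysis.** The next paragraph gives as its examples "a dose administration record with missing end date, or last date of study treatment is after the cut-off date". In these cases "the end date will be imputed to the cut-off date in order to calculate e.g., the duration of exposure to study treatment". It adds: "The imputed date will be displayed and flagged in the listings".

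The second rule is not limited to patients alive or on treatment at cut-off, and it contains no earliest-of condition.

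Three definitions elsewhere in the SAP depend on the last treatment date:

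- SAP 2.8.1 states: "Last date of exposure to LTT462 is the last date of study treatment". It derives duration of exposure as last date minus first date plus 1, with interruptions not excluded.
- SAP 2.2 sets the on-treatment interval as "from the start date of LTT462 treatment until the last date of LTT462 treatment + 30 days inclusive".
- SAP 2.2 also defines the last treatment date as the last date on which a non-zero dose was actually given and entered on the Dosage Administration Record.

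**The concern.** Imputing to the cut-off is sensible when the end date is missing because treatment is continuing. It is wrong when treatment ended earlier and the date was simply not captured. SAP 6.2 recognises this for adverse events and concomitant medications by stopping them at death, but gives dose records a different result.

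The final CSR makes the gap plainer. SAP 2.1 plans it for when all patients have discontinued the study. By then nobody should still be on treatment, so the rule would assign too late a date to essentially every missing dose end date it reaches.

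Duration of exposure is directly affected. Cumulative dose, dose intensity and relative dose intensity are summarised over the same treated period, and dose intensity is one of the primary tolerability endpoints (SAP 1.2 and 2.9.1). If the imputed date also serves as the last treatment date for the 30-day window, it could affect which adverse events and deaths enter the on-treatment tables in SAP 2.11.1.

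**Working it through.** The plan gives no figure to reproduce. The check applies the SAP's own definitions to one patient.

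**Inputs from the documents**
- Duration of exposure = last date − first date + 1 (SAP 2.8.1).
- Relative dose intensity (RDI) = cumulative dose / cumulative planned dose (SAP 2.8.1).
- On-treatment window end = last treatment date + 30 days (SAP 2.2).
- Cut-off at day 168: six cycles (SAP 2.1) of 28 days (Protocol 7.1.4), 6 × 28 = 168. Using this minimum follow-up as the patient's cut-off day is an assumption.

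**Assumed patient (not from the documents)**
QD dosing at a constant dose, first dose day 1, true last dose day 40, 10 missed days, death on day 90, dose end date missing. Imputed days are counted as dosed, and one dose is planned per day.

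| End date used | Exposure (days) | RDI | Window would end | Day-90 death inside window? |
|---|---|---|---|---|
| True last dose, day 40 | 40 − 1 + 1 = 40 | 30/40 = 0.75 | day 70 | no |
| Capped at death, day 90 | 90 | 80/90 = 0.89 | day 120 | yes |
| SAP 6.2 as written, day 168 | 168 | 158/168 = 0.94 | day 198 | yes |

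**Duration.** The written rule adds 168 − 40 = 128 days beyond the true last dose, of which 168 − 90 = 78 fall after death. The overrun past death is always cut-off minus death date. For a death on day 90 it is 10, 78, 275 or 640 days with the cut-off at day 100, 168, 365 or 730.

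**RDI.** The value moves into the SAP's 0.9 to <1.1 category. Removing the C1D2 dose that the protocol omits gives 29/39 = 0.74 and 157/167 = 0.94, so the shift remains. It depends on the missed doses, however. With none missed and no dose change, RDI is 40/40 = 168/168 = 1 under either date, and dose intensity is likewise unchanged.

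**Group summary.** An excess of 128 days in one patient raises the mean exposure of a group of 3 by 128/3 = 42.7 days, and of a group of 6 by 128/6 = 21.3 days. The median, which is also reported, is less sensitive.

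**Window.** The last two columns apply only if the imputed date is taken as the last treatment date. In that case a cap at death alone would remove exposure after death but would still classify this death as on-treatment.

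**The case against.** Several counter-arguments have force.

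- **The death rule could be read more widely.** Its examples of events are not exhaustive, so a sponsor could say that dose records were meant to be included. That reading does not survive the next paragraph, which names dose records and sends them to the cut-off.
- **The on-treatment window may be unaffected.** A reader might infer that the rule turns post-treatment events and deaths into on-treatment ones. The documents do not establish that. SAP 2.2 requires a dose that was given and recorded, which an imputed date is not, and SAP 6.2 imputes only where a specific analysis needs it. Against this, SAP 2.8.1 equates the last exposure date with the last treatment date. The effect is possible, not stated.
- **The primary endpoint may be untouched.** Duration and cumulative dose are not primary endpoints. Dose intensity and RDI are ratios and change only when doses were missed or altered. SAP 2.8.1 also defines cumulative dose by doses taken, so it is not certain that imputed days would count. This stands.
- **The trigger is a data-cleaning failure.** All doses and changes must be recorded (Protocol 6.1.1 and 6.3.1), missing values are queried and data verified before lock (Protocol 9.4), and imputed dates are flagged. This makes the case rare. Flagging in a listing does not correct a summary table.
- **A companion document was not available.** SAP section 1 places derived-variable specifications in the Programming Datasets Specifications. A cap there cannot be excluded.

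A reader might also take the span from first patient first visit (15 April 2016) to the SAP date (13 May 2019), 1,123 days or about 160 weeks, as the size of the error. That is only an outer limit. It assumes a cut-off near the SAP date, which no text states, and treats first visit as first dose.

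**Conclusion.** The point holds for duration of exposure. As written, SAP 6.2 gives too long a duration for any patient who died or permanently stopped before the cut-off and whose dose end date is missing, and the visible text contains no cap. Only the missing-end-date trigger is at fault: truncating treatment that continues past the cut-off is correct.

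The effect on cumulative dose, dose intensity and RDI is conditional on how imputed days are counted and, for the two ratios, on missed or changed doses. The effect on on-treatment events and deaths depends on an unstated choice of date. A 30-day window that extends beyond the death of a patient who dies on treatment is normal and is not part of this criticism.

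Frequency is probably low. The consequence of one case can still be visible, because cohorts have 1 to 6 patients (Protocol 6.2.3.2), although pooling of cohorts at the same dose and regimen dilutes it. The 128-day excess and the 0.75 to 0.94 shift in RDI belong to the assumed patient and are not forecasts. The point merits correction before database lock because the stated rule is wrong for these patients and the remedy is small.

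**What to change.** Amend SAP 6.2 so that a missing dose end date is imputed to the earliest of:

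- the cut-off date;
- the date of death;
- the recorded last dose date or, if that is unavailable, the permanent treatment discontinuation date.

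The order of preference in the last item matters. Protocol 7.1.5 separates the last dose from the decision to discontinue, so a discontinuation date can fall after the last dose and still overstate exposure somewhat.

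Add one sentence saying whether this imputed date, or only the last recorded non-zero dose, defines the 30-day on-treatment window, and align SAP 2.2 and 2.8.1 with that choice.

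The cost is a sentence or two in the SAP and a minimum-of-dates step in the derivation. No new data collection is needed: the protocol already provides a Death form (8.1.1), recording of treatment discontinuation with an end-of-treatment visit (7.1.5), and the Dosage Administration Record. If the Programming Datasets Specifications already contain such a cap, it need only be carried into the SAP.
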